10.1.7 Delayed chemotherapy

Chemotherapy will be delayed if, after a course of chemotherapy, the patient has failed to meet the criteria for the next course, and treatment will then be suspended for up to 2 weeks. Then, after 2 weeks, treatment will be halted if patients still do not meet the criteria for the next course of chemotherapy. Before the next course of chemotherapy, patients will undergo relevant laboratory examinations once a week and their recovery will be evaluated by the investigators. Chemotherapy will be reinstated if patients recover and meet the criteria for the next course of chemotherapy. The chemotherapeutic dosage will be adjusted if necessary.

10.1.8 Regular evaluation during and after preoperative CRT

Regular evaluation will consist of: routine blood tests once a week; liver and kidney function before and after chemotherapy; esophageal barium x-ray examination after the patient received radiotherapy with 20 Gy and 40 Gy. All patients underwent clinical re-staging approximately 4-6 weeks after the completion of CRT, including physical examination, standard laboratory tests, EGD with EUS, pulmonary function tests, Esophageal barium x-ray, and neck/chest/abdominal CT with contrast.

10.1.9 Timing of surgery

Approximately 4–6 weeks after completion of CRT, surgery will be performed if the patient's white blood cells, platelets, and liver and kidney function have all returned to normal. Routine blood tests, blood biochemical examinations, chest and abdominal CT scans, detection of lung function, and electrocardiograms will be performed before surgery.

10.1.10 Surgical procedures

The two groups undergo the same surgical procedure specified as followed.

10.2 Protocol for patients receiving surgery alone

Surgery will be conducted soon after the randomization. McKeown or Ivor Lewis esophagectomy will be performed. Two-field lymphadenectomy with total mediastinal lymph node dissection is performed during sugery. Radical resection will be defined by both macroscopic observation and postoperative pathological negative margin. A jejunum tube will be placed via the nose or by jejunostomy.

The lymph nodes resected during total lymphadenectomy include the left recurrent laryngeal nerve nodes, right recurrent laryngeal nerve nodes, infraaortic arch nodes, periesophageal nodes of the upper, middle and lower thoracic portion, the infracarinal nodes, the posterior mediastinal nodes, the paracardiac nodes, lesser curvature nodes, the left gastric nodes, the common hepatic nodes, the splenic nodes and the celiac nodes.

10.3 Pathology

The resection specimens will be macroscopically and microscopically reviewed by a team of experienced pathologists using the standard protocol (margins, tumor type and extension, lymph nodes). The lymph node dissection should contain at least 15 nodes. For patients receiving preoperative CRT, the pathological response will be defined according to the tumor regression grade, as described by Mandard et al. In the absence of macroscopic tumor, the whole resected tissue was embedded in paraffin to make an assessment for the presence of any residual tumor. Pathologic complete response (pCR) was defined as the absence of residual tumor within the esophagus and lymph nodes.

The pathology report should contain the following: site of the tumor/lesion, type and grade of the tumor, extension into the esophageal wall, resection margins, therapy effects (Mandard score), lymph node status including the site, and the number of nodes with therapy effects.

Tumor Response Grading Systems (Mandard score)

Grade 1: Complete regression;

Grade 2: Isolated cell nests;

Grade 3: More residual cancer cells but fibrosis still predominates;

Grade 4: Residual cancer outgrowing fibrosis;

Grade 5: Absence of regressive changes.

11.0 ETHICS

11.1 Informed consent

Before patients recruitment, investigator should completely and comprehensively explain the objective of this study, the characteristics of drugs, and the potential toxicity and risk in the treatment, and allow the patients to be aware of their rights, risks and benefits. Informed consent form should be signed before recruitment and preserved in files as paper documentation.

11.2 Ethics and policy

This study will be conducted according to the Declaration of Helsinki (2000), Good Clinical Practice (GCP) published by CFDA and other relevant regulations. The study must be approved by the Ethics Committee from leading center and each participating institution. Any amendments of the study protocol should be re-approved by the Ethics Committee during the study.

12.0 DATA PROCESSING AND PRESERVATION

12.1 CRF

CRF (Case Report Form) should be timely filled in to assure accuracy and timely summary. CRF should not be obliterated. If there is mistake, the investigator should sign at the site of obliteration (see the introductions to filling in CRF). Three copies of CRF should be obtained to turn over to the leading site, sponsor and local site after the study. Data will be input into database after reviewing by the CRA. Then all of data cannot be altered.

12.2 Establishment of database

Once the CRF is received by the statisticians, the queries about the data should be answered by communicating with the investigator who fills in the CRF. The statisticians should timely establish database which is then reviewed and locked by the major investigators, sponsor, statisticians and CRA. Irrelevant persons are not accessible to the database and unable to alter the database. All the data should be backed up.

12.3 Preservation of materials

The investigators should preserve the documentations properly. According to the GCP, the documentations should be preserved by the investigators for more than 5 years.

13.0 STATISTICAL ANALYSIS

All patients will be included in the analysis whether they complete the treatment protocol or not. Data analyses will be done according to the 'Intention to treat' principle.

13.1 Sample size

The primary endpoint in this study is overall survival. We have the following set of hypotheses:

 H_0 : The study group has the same median survival of 39 months as the Control group;

H_i: The median survival of the study group and control group are different. Sample size are calculated according to a projected median survival of 56 months and 39 months for patients assigned to multimodality treatment arm and surgery alone arm, respectively. We assumed an overall two-sided significance level of 5% and a statistical power of 80%. The randomization ratio between the experimental and control arms is 1:1. With 7 years' accrual, 2 years' follow-up, and two planned interim analyses, the calculated sample size will be 392 patients, 196 patients per arm^[10]. Assuming that 10% will drop-out, the intended number of randomized patients will be 430, 215 per arm. Two interim analyses by an independent safety and data monitoring committee will be done after 107 patients (25%), and 430 patients (100%) have been enrolled.

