13.3 Analyses of secondary endpoints

Disease-free survival (DFS) is defined as the time period from the date of R0 resection to the date of disease recurrence or death will be calculated as disease-free survival (DFS). DFS will be calculated using the Kaplan-Meier method, and then compared by the log-rank test. The rate of R0 resection, incidence of complications, and peritreatment mortality will be compared with the Chi-square test (or Fisher's exact test, if indicated).

13.4 *P* value

According to the O'Brien-Fleming algorithm, the two-sided significance level will be 0.000527 in the first interim analysis and 0.014 in the second interim analysis. The final significance level will be 0.045.

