13.5 Interim analysis

- 13.5.1 An independent Data Monitoring Committee will be appointed to monitor the study and make decisions regarding possible early closure and publication.
- 13.5.2 The Committee will meet at least once a year (or discuss via electronic means) to ensure no undue toxicity and to monitor the data quality and results. Only this committee will be allowed access to the data until the decision is made to release the results.
- 13.5.3 Two formal interim analyses will be performed on 1 June, 2011 and 31 December, 2015.
- 13.5.4 The interim analysis of survival and toxicities will be reviewed by the committee. These results will not be the sole criteria for deciding whether to terminate accrual or report results early. All decision will also take into account the characteristics of patients, the nature of any toxicity, relevant external results, and other pertinent information.
- 13.5.5 Reports of the results will be made corresponding to the required number of events in the sample size calculation section of the protocol (about universal 2-year follow-up), and again after universal 5-year follow-up.
- 13.5.6 An Executive Committee composing of all the study coordinators will meet (or discuss via electronic means) every 6 months to monitor the patient accrual rate and to solve practical problems encountered during conduction of the trial.
- 13.5.7 Earlier and more frequent meetings will be called if excessive toxicities are observed.

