Appendix

Modifications of the Study Protocol

Date	Before modification	After modification	Location
October 20, 2011	6.1 Inclusion criteria d. Patients aged from 18 to 60	6.1 Inclusion criteria d. Patients aged from 18 to 70	P8
October 20, 2011	13.5 Interim analysis 13.5.1 The Office of Good Clinical Practice from Sun Yat-sen University Cancer Center will monitor the study and make decisions regarding possible early closure and publication Interim analysis.	13.5 Interim analysis 13.5.1 An independent Data Monitoring Committee will be appointed to monitor the study and make decisions regarding possible early closure and publication.	P19
June 26, 2013	13.1 Sample size: 640 patients should be enrolled	13.1 Sample size: 430 patients should be enrolled	P18
December 1, 2015	13.3 Analyses of secondary endpoints The rate of R0 resection will be compared by the t test.	13.3 Analyses of secondary endpoints The rate of R0 resection will be compared by the Chi-square test.	P18

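### The interim levels 0.000527 / 0.014 / 0.045 fit looks at one third and two thirds of the deaths, but the looks are timed by enrolment in one section and by calendar date in another

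*Protocol*

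**What the plan says.** The protocol deals with the interim looks in three places.

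- **Levels (section 13.4).** Citing O'Brien-Fleming, it says "the two-sided significance level will be 0.000527 in the first interim analysis and 0.014 in the second interim analysis". The final level is 0.045.
- **Timing by enrolment (section 13.1).** The two looks "will be done after 107 patients (25%), and 430 patients (100%) have been enrolled".
- **Timing by date (section 13.5.3).** "Two formal interim analyses will be performed on 1 June, 2011 and 31 December, 2015".

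No section ties an interim look to a number or fraction of deaths. Section 13.5.5 times the main report by a required number of events that it says is in the sample size section, but 13.1 gives none. The primary analysis is a log-rank test of overall survival (13.2), planned on a "projected median survival of 56 months and 39 months for patients assigned to multimodality treatment arm and surgery alone arm", with an overall two-sided level of 5% and 80% power.

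**The concern.** The information in a log-rank test is, to a close approximation, proportional to the number of deaths. A set of O'Brien-Fleming levels is therefore right only for the death fractions at which it was computed. Neither enrolment nor the calendar fixes those fractions. If the looks fall elsewhere, the printed levels are not the O'Brien-Fleming boundary for the looks actually held. The bar may then be too strict or too lenient, and the overall level need not be exactly 5%.

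The timing is also stated twice, by different rules, with nothing to say which one governs. For analyses that can lead to early reporting of the primary endpoint, that choice should be fixed in advance.

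**Working it through.** **Inputs from the protocol.** Medians of 39 and 56 months, 1:1 allocation, 430 patients, 7 years' accrual plus 2 years' follow-up (13.1). Start on 1 July 2007 (3.0). Recruitment to December 2014 (annual plan after section 15).

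**Assumptions of mine.** Exponential survival, uniform accrual unless stated, no censoring for drop-out.

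**Step 1: reproduce the printed levels.** The classical O'Brien-Fleming boundary is z_k = C/√t_k, where t_k is the fraction of deaths and C is solved so that the two-sided crossing probability is 0.05. For t = 1/3, 2/3, 1:

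- C = 2.004
- z = 3.471, 2.454, 2.004
- p = 0.00052, 0.0141, 0.0451

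These match 13.4 apart from a trivial difference in the first. A Lan-DeMets O'Brien-Fleming-type spending function at the same fractions gives 0.0002, 0.012 and 0.046, so it is not the source.

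**Step 2: required deaths.** HR = 39/56 = 0.696. Schoenfeld: 4(1.960 + 0.842)²/(ln 0.696)² ≈ 240. An allowance of about 1.7% for the two looks gives 240 × 1.017 ≈ 244. With a mean death probability of 0.600, about 400 patients are needed, which agrees with the stated 392 within 3%.

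**Step 3: expected deaths at each look.** The hazards are λ = ln 2/39 = 0.0178 and ln 2/56 = 0.0124 per month. For accrual over R months and a = min(T, R), the death probability by month T among those enrolled is 1 − [exp(−λ(T−a)) − exp(−λT)]/(λa), averaged over the arms. With R = 84:

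- 107th patient: month 107/430 × 84 = 20.9; 107 × 0.142 ≈ 15 deaths
- 1 June 2011: month 47; 241 enrolled × 0.282 ≈ 68 deaths
- 430th patient: month 84; 430 × 0.429 ≈ 185 deaths
- 31 December 2015: month 102; 430 × 0.563 ≈ 242 deaths
- Planned end: month 108; 430 × 0.600 ≈ 258 deaths

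**Step 4: matching levels, and overall alpha with the printed levels.** The slow-start rows assume 107 patients by month 47 and 430 by month 90.

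| Timing | Deaths: look 1 / look 2 / end | Fractions | C | Matching level, look 2 | Matching level, final | Alpha with printed levels |
|---|---|---|---|---|---|---|
| Enrolment, 84-month accrual | 15 / 185 / 258 | 6% / 72% | 2.010 | 0.0175 | 0.044 | 0.049 |
| Enrolment, 90-month accrual | 16 / 193 / 264 | 6% / 73% | 2.013 | 0.019 | 0.044 | 0.049 |
| Dates, 84-month accrual | 68 / 242 / 258 | 26% / 94% | 2.022 | 0.037 | 0.043 | 0.0455 |
| Dates, 90-month accrual | 63 / 232 / 264 | 24% / 88% | 2.026 | 0.031 | 0.043 | 0.046 |
| Slow start, look 2 at month 90 | 30 / 151 / 235 | 13% / 64% | 1.999 | 0.013 | 0.046 | 0.0505 |
| Slow start, look 2 at month 102 | 30 / 197 / 235 | 13% / 84% | 2.025 | 0.027 | 0.043 | 0.047 |

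At look 1 the matching level is about 1e-16 under the enrolment rule and 0.00004 to 0.00008 under the dates. With 15 deaths, reaching p < 0.000527 (z = 3.467) needs an observed HR of about exp(−2 × 3.467/√15) ≈ 0.17.

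**Sensitivity to the denominator.** Against 244 required deaths rather than 258 projected, the 84-month fractions become 15/244 = 6% and 185/244 = 76% by enrolment, and 68/244 = 28% and 242/244 = 99% by date. On that count the second dated look is practically the final analysis.

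**Sensitivity of alpha.** With the printed levels, overall alpha is about 0.0525 if look 2 falls at 50% of the deaths and 0.054 at 40%.

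**The case against.** The strongest reply is that error control is hardly touched. The levels were fixed in advance, and at every projected timing overall alpha lies between about 0.0455 and 0.0505. This stands. A reader might infer from the mismatch that the trial's 5% level is broken, but the figures do not support that. Alpha would exceed 5% by more than a trace only if the second look came well before two thirds of the deaths, and neither rule points there.

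Three other stronger readings also fail.

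- **That the enrolment counts and the dates contradict each other.** Under uniform accrual the 107th patient comes in about spring 2009, and about 225 to 241 are enrolled by 1 June 2011. But the protocol never states uniform accrual. A slow start could bring the first pair together, and a date one year after recruitment closes is still after 430 patients. What the text does show is two triggers with no order of precedence.
- **That no usable look occurs during accrual.** By date, the first look falls during recruitment with about 63 to 68 deaths. The second look follows full enrolment, but 13.5.4 speaks of "deciding whether to terminate accrual or report results early", and it can still serve the second purpose.
- **That no proper body existed for the 2011 look.** The independent committee enters through an October 2011 entry in the Appendix. That log describes superseded text, and it names the office that monitored before then.

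It is also fair to say that under the enrolment rule the second-look discrepancy is modest (about 0.018 against 0.014). Only the date rule makes the printed bar much too strict.

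**Conclusion.** The point holds as a mismatch between levels and looks, and it should be fixed. The printed levels are correct for one third and two thirds of the deaths, and neither stated trigger delivers those fractions in any scenario computed. Under uniform accrual the second look is held to 0.014 where O'Brien-Fleming would allow about 0.018 (enrolment) or 0.031 to 0.037 (dates). A benefit with a p-value in between would not be declared at that look. Under the enrolment rule the first look is close to uninformative.

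The cost is some unspent alpha and uncertainty about when the looks are due, not a false-positive rate materially above 5%. The reproduction of the levels needs no assumption about survival or accrual. The death counts and fractions rest on exponential survival, the accrual pattern and no drop-out censoring, and should be read as approximate.

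**What to change.** 1. In 13.1, state the required number of deaths (about 240 to 244 on the stated assumptions), so that the reference in 13.5.5 has a target.
2. State one governing trigger for the looks, preferably a death count, and remove or subordinate the other in 13.1 and 13.5.3.
3. In 13.4, set each remaining level, including the final one, from a Lan-DeMets O'Brien-Fleming-type spending function at the actual death counts. Any look already held should enter with its own death count. The Appendix carries an entry of 1 December 2015, so this text post-dates the first dated look, and simply moving that look to one third of the deaths is no longer open.
4. Keep the printed levels only if the looks are in fact held at one third and two thirds of the required deaths (80 and 160 of 240, or 81 and 163 of 244).

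The cost is wording and a small recalculation, with no extra patients. Looks driven by deaths have less predictable dates, which makes committee meetings harder to schedule.

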13.2 Analysis of the primary endpoint

Overall survival (OS) is defined as the time period from the date of randomization to the date of death or the last follow-up. OS including 3-year and 5-year survival rates will be calculated using the Kaplan-Meier method, and then compared by the log-rank test.

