8.0 STRATIFICATION / RANDOMIZATION SCHEME

8.1 Stratification

Patients will be stratified according to the treatment centers (SYSUCC vs. SUMCCH vs. TZH vs. SHCH vs. TJMUCH vs. FUSCC vs. ZJCH vs. SCH).

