8.2 Randomization

Eligible patients will be randomized using a 1:1 allocation of patients to ARM1 and ARM2. Stratification factors for the randomization are centers defined in Section 8.1. The block sizes will be chosen by the statistician so that each block contains the patients in equal proportion. This procedure helps to ensure both randomness and investigator blinding (the block sizes are known only to the statistician), as recommended by Friedman et al^[9].Randomization will be generated by the statistician in sealed envelopes labeled by stratum. Only after the registration, the envelopes will be opened. Every patient will have a corresponding unique subject number during the whole study.

Eligible patients will be randomized to either:

ARM 1: Preoperative Chemoradiotherapy followed by Surgery or

ARM 2: Surgery alone.

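### Randomisation is blocked within eight centres, but 13.2 names a log-rank test without centre: valid, but conservative and less powerful if survival differs between centres, and not a test of 3- and 5-year rates

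*Protocol*

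**What the plan says.** **Randomisation.** Protocol 8.1 names eight centres as strata: "Patients will be stratified according to the treatment centers (SYSUCC vs. SUMCCH vs. TZH vs. SHCH vs. TJMUCH vs. FUSCC vs. ZJCH vs. SCH". Section 8.2 confirms that this is the scheme used: "Stratification factors for the randomization are centers defined in Section 8.1". Allocation is 1:1 in blocks, with sealed envelopes labelled by stratum. No other stratification factor is named.

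**Primary analysis.** Section 13.2 reads: "OS including 3-year and 5-year survival rates will be calculated using the Kaplan-Meier method, and then compared by the log-rank test". It does not say whether the test is stratified. Centre appears nowhere in section 13.

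**Planning.** Section 13.1 rests on a "projected median survival of 56 months and 39 months for patients assigned to multimodality treatment arm and surgery alone arm, respectively" and states: "We assumed an overall two-sided significance level of 5% and a statistical power of 80" percent. It gives 392 patients before drop-out and 430 after. No centre effect enters that calculation, and the hypotheses are worded as medians.

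**The concern.** There are two matters in one sentence of 13.2.

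First, blocking within centre forces the arms to be balanced on centre. If centre is prognostic, that balance makes the treatment comparison more precise. The unstratified log-rank does not use this precision: its variance is computed as if centre had been left to chance. The rejection rate under the null then falls below the nominal level, and power falls with it. At stake is power in a trial planned at 80%, where a remedy needs no extra patients or data.

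Second, the sentence places the 3- and 5-year survival rates among the things compared by the log-rank. That test addresses equality of the whole curves. A p value from it, printed beside a difference in 5-year rates, answers a different question from the one the reader will think it answers.

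**Working it through.** **1. Inputs.** From 13.1: medians 56 and 39 months, two-sided 0.05, power 80%, 1:1 allocation, 84 months' accrual, 24 months' further follow-up, 392 patients. From 8.1: eight centres. Not in the protocol and therefore assumed: exponential survival, uniform accrual, block size 4, centre sizes, and the SD of the centre log-hazards.

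**2. The plan's own figure, without centre.**
- HR = 39/56 = 0.696, and ln HR = −0.362.
- Events (Schoenfeld) = 4(1.960 + 0.842)² / 0.362² = 240.
- With hazard λ = ln 2/median, accrual A = 84 and follow-up F = 24, the event probability is 1 − [exp(−λF) − exp(−λ(A+F))]/(λA). This is 0.661 for control and 0.538 for the experimental arm, mean 0.5995.
- N = 240/0.5995 = 400, which is 2.1% above the stated 392. At 392 patients, 235 events are expected and power is 79.2%.

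So 392 is reproduced closely by a log-rank that takes no account of centre.

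**3. The two tests.** Let U be observed minus expected deaths in one arm and V its hypergeometric variance. The unstratified test is Z = U/√V over all patients. The stratified test is Z = ΣUₖ/√(ΣVₖ), with Uₖ and Vₖ computed within centre k.

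**4. Simulation.** There were 10,000 trials per setting, with N = 392 and blocks of 4 within centre. Centre effects on the log-hazard were normal with the SD shown, and each test was at two-sided 0.05. Centres were either equal (49 each) or uneven (180, 70, 50, 32, 24, 16, 12, 8). Monte Carlo error is about 0.2 points on type I error and 0.4 to 0.5 on power.

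| SD | Centres | Type I error %, unstratified / stratified | Power %, unstratified / stratified | Gain from stratifying (points) |
|---|---|---|---|---|
| 0 | equal | 4.7 / 4.9 | 78.8 / 78.0 | −0.9 |
| 0 | uneven | 5.0 / 5.1 | 79.3 / 78.4 | −0.9 |
| 0.2 | equal | 5.1 / 5.3 | 77.2 / 77.2 | 0.0 |
| 0.2 | uneven | 5.0 / 5.3 | 78.6 / 78.5 | −0.1 |
| 0.4 | equal | 4.5 / 5.3 | 75.2 / 77.8 | 2.6 |
| 0.4 | uneven | 4.2 / 4.9 | 75.3 / 77.4 | 2.1 |
| 0.6 | equal | 3.0 / 4.6 | 69.9 / 77.4 | 7.6 |
| 0.6 | uneven | 4.2 / 5.6 | 70.7 / 77.3 | 6.6 |
| 0.8 | equal | 2.4 / 5.1 | 62.1 / 76.2 | 14.1 |
| 0.8 | uneven | 2.8 / 5.3 | 64.4 / 75.9 | 11.5 |

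(Gains are taken before rounding.)

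A second simulation used 430 patients, uneven centres, 10% lost, the final level of 0.045 from 13.4 and 2,500 trials per setting. Power, unstratified against stratified, was 79.6% vs 78.5% with no centre differences, 78% vs 79% at SD 0.3, 74% vs 78% at 0.5 and 69% vs 78% at 0.7. The pattern is the same.

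**5. What the SD means.** The hazard ratio between a centre one SD above the mean and one SD below is exp(2·SD): 1.5 at 0.2, 2.2 at 0.4, 3.3 at 0.6 and 5.0 at 0.8.

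**6. Fixed-time rates.** With S(t) = 0.5^(t/median), the planning medians give 52.7% vs 64.0% at 36 months and 34.4% vs 47.6% at 60 months. The log-rank sums over all event times and does not test either gap.

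**The case against.** **Silence is not a choice.** The words of 13.2 would also fit a stratified log-rank, and a statistical analysis plan that is not at hand may specify one. This stands as a limit: the mismatch is in the protocol as written, and it disappears if that plan already stratifies. The protocol does, however, name its primary test, and an unqualified log-rank is ordinarily read as unstratified.

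**The loss may be nil.** A reader might infer that power is certainly lost. The documents do not support that. They give no between-centre figure, and with no centre differences the unstratified test is about 1 point better. Entry limits on histology, stage, age and performance status (6.1) and a common surgical protocol (10.2) give no reason to expect the high end of the range. In the other direction, two operations, two cisplatin schedules, optional PET-CT and a mix of stages IIB and III leave room for centres to differ. Neither side settles the SD.

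**Validity is intact.** A reader might infer that the primary test is unsound. It is not: its type I error is at or below nominal, within simulation error, throughout the table.

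**The hazard ratio is not biased.** In the second simulation at SD 0.5, the average unstratified HR was 0.715 against 0.695 stratified. A reader might call this dilution. It is the usual contrast between a marginal and a within-centre hazard ratio, which are different targets, and 13.2 names no HR estimator.

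**The 3- and 5-year wording is a stock phrase.** Section 13.3 uses much the same words for DFS without any fixed-time rate. No hypothesis, alpha or sample size rests on the rates, so this part is minor. The literal reading still invites a misplaced p value.

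**Conclusion.** The point holds in a conditional form. Randomisation is stratified by centre and the primary test, as the protocol words it, is not. The test controls type I error. If survival differs between centres it is conservative and gives up power: about 0 points at an SD of 0 to 0.2, 2 to 3 at 0.4 and 7 to 8 at 0.6. The 0.8 setting (12 to 14 points) needs a fivefold spread in hazard between centres one SD either side of the mean, and nothing in the protocol supports that. All these figures rest on the assumed SD, centre sizes, block size and exponential survival.

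The change is still worth making because the balance is uneven: at most about 1 point is given up if centres are alike, against several points saved if they differ moderately. The trial has little to spare, since the stated 392 yields 79.2% at the 0.05 level without any centre effect.

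The wording on the 3- and 5-year rates is a real but minor fault, on which no trial decision depends.

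**What to change.** In 13.2, unless the statistical analysis plan already does so:

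1. Name the primary test as a log-rank stratified by randomisation centre, and use the same test at the interim analyses.
2. Fix in advance a rule for pooling very small centres, based on size alone and set without sight of outcomes by arm. A stratum with patients at risk in only one arm adds nothing to the test.
3. Take any reported hazard ratio and its confidence interval from a Cox model stratified in the same way. Adjusting for clinical stage is an optional extra that this point does not require, since stage is not a stratification factor.
4. Report the 3- and 5-year Kaplan-Meier rates by arm and their differences with confidence intervals from Greenwood standard errors. State that the log-rank p value refers to the whole curves and is not attached to those rates.

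The cost is a short rewording of 13.2. Centre is already recorded for randomisation, so no new data are needed. The statistical price is about 1 point of power if centres do not differ at all.

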6.0 PATIENT SELECTION

6.1 Inclusion Criteria

- a. Patients diagnosed with potentially resectable stage IIb or III thoracic esophageal squamous cell carcinoma (according to the 6th AJCC edition).
- b. With no previous treatment.
- c. With at least 6-month expected survival.
- d. Patients aged from 18 to 70.
- e. Adequate marrow: white blood cell $\geq 4.0 \times 10^9 / L$; neutrophil $\geq 1.5 \times 10^9 / L$; platelet $\geq 100.0 \times 10^9 / L$; hemoglobin ≥ 90 g/L.
- f. With normal liver and kidney function.
- g. Satisfactory performance status: Karnofsky performance score (KPS) \geq 90.
- h. Informed consent will be obtained before the study.

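### The primary OS log-rank test names no stratum or covariate, although clinical stage (IIB vs III) is known for every patient at randomisation; using stage would gain about 1 to 7 points of power if the stage hazard ratio is about 1.5 to 2.5.

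*Protocol*

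**What the plan says.** - **Primary test (13.2).** Overall survival "will be calculated using the Kaplan-Meier method, and then compared by the log-rank test". No stratum or covariate is named.
- **Eligibility (6.1).** Patients must have "potentially resectable stage IIb or III thoracic esophageal squamous cell carcinoma". Under section 5.0 and the schema this runs from T1N1 to T4: IIB is T1-2N1, III is T3N1 or T4.
- **Timing of staging (9.1, 9.2).** CT and endoscopic ultrasound are done before recruitment, and randomisation follows the eligibility assessment. Stage is therefore fixed for each patient before allocation.
- **Randomisation (8.1, 8.2).** "Patients will be stratified according to the treatment centers". Centre is the only factor, with eight centres.
- **Design (13.1, 13.4).** Sample size rests on a "projected median survival of 56 months and 39 months for patients assigned to multimodality treatment arm and surgery alone arm", two-sided 5% and 80% power. "With 7 years' accrual, 2 years' follow-up, and two planned interim analyses", "the calculated sample size will be 392 patients, 196 patients per arm", raised to 430 for 10% drop-out. The final significance level is 0.045.

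**The concern.** When a factor that affects survival is left out of a log-rank comparison, patients with different underlying hazards are pooled in the same risk sets. If treatment acts proportionally within stage, the pooled comparison has less power than one made within stage. The calculation in 13.1 uses one exponential curve per arm and makes no allowance for such heterogeneity. Stage is also left to chance in the allocation, so in any single trial a stage imbalance feeds into the unadjusted comparison. At stake are a few points of power on the primary endpoint, recoverable from a variable that eligibility already requires.

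**Working it through.** **1. The plan's own figure.** With exponential survival, HR = 39/56 = 0.696 and ln HR = -0.362.

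- Events (Schoenfeld): 4 × (1.960 + 0.842)² / 0.362² ≈ 240.
- Probability of death with hazard λ = ln 2/median, 84 months' uniform accrual and 24 months' further follow-up: 1 - (e^(-24λ) - e^(-108λ))/(84λ). This is 0.661 for median 39 and 0.538 for median 56; mean 0.5995.
- N = 240/0.5995 ≈ 400, against 392 stated (within 3%).
- Power at 392: 392 × 0.5995 = 235 events; √235/2 × 0.362 - 1.960 = 0.81, so 79.2%.

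The design reproduces for a plain log-rank test with no stage effect.

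**2. Adding stage.** Assumed, because the documents give no value: stage III vs IIB hazard ratio 1.2 to 3.0 and stage III share 30%, 50% or 70%. Survival is exponential within stage, the treatment HR is 0.696 in both stages, and the control-arm median is 39 months. The setting below has 430 patients, 10% lost to follow-up at a random time and two-sided 0.045, with 20,000 simulated trials per cell. Ranges are over the three stage shares.

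| Stage HR | Plain log-rank | Stratified by stage | Gain (points) |
|---|---|---|---|
| 1.2 | 79.4–79.7% | 79.3–79.8% | 0 to 0.2 |
| 1.5 | 77.7–78.9% | 78.7–79.7% | 0.8 to 1.3 |
| 2.0 | 75.5–76.2% | 78.9–79.4% | 2.8 to 3.9 |
| 2.5 | 71.8–74.6% | 78.8–79.8% | 5.2 to 7.1 |
| 3.0 | 68.2–71.9% | 78.3–79.1% | 7.3 to 10.1 |

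With 392 patients at 0.05 the gains are much the same: about 0 to 0.6 points at stage HR 1.3, 1 at 1.5, 3 to 4 at 2.0, and 5 to 7 at 2.5.

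**3. Does the gain come only from holding the within-stage HR at 0.696?** No. With the treatment effect reset so that the plain test has about 80% power (392 patients), the gains are about 1, 3 to 4 and 4 to 6 points at stage HR 1.5, 2.0 and 2.5.

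**4. Stratified log-rank or adjusted Cox.** With 60% stage III, 430 patients, no loss and 0.045, power for plain / stratified / stage-adjusted Cox is 80.1 / 81.1 / 81.1% at stage HR 1.5, 76.1 / 79.7 / 79.8% at 2.0, and 75.2 / 80.9 / 81.0% at 2.5. The two adjusted forms are interchangeable.

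**5. Type I error.** In 15,000 null trials at nominal 0.045: plain 0.043, stratified 0.046, Cox 0.046.

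**6. Crossing stage with centre.** In a separate set of 6,000 trials at stage HR 2.0 and 60% stage III, power was 78.2% plain, 81.2% stratified by stage and 79.1% stratified by 8 centres × 2 stages. Crossing cuts the gain from 3.0 to 0.9 points. (Power levels differ by up to about 2 points between steps 4 and 6; the comparison within each set is what matters.)

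**7. Chance imbalance.** The SD of the between-arm difference in stage III share is √(2p(1-p)/215), or 4.6 to 4.8 points for p between 0.65 and 0.50. One trial in 20 exceeds 1.96 × 4.7 ≈ 9 points. At stage HR 2.0 that shifts the unadjusted log HR by about 0.093 × ln 2 ≈ 0.065, half of its standard error (2/√255 ≈ 0.125).

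**The case against.** The strongest reply is that strata and covariates are usually left to the SAP, which is not shown, and that 13.2 does not say the test is unstratified. The SAP may well name strata. But 13.2 itself states the primary test; if the SAP stratifies by stage, the two texts should be made to agree, and if it does not, the point applies.

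Several stronger readings are tempting and do not hold.

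- **That the plain test is wrong or biased.** Randomisation keeps it valid, and its type I error already covers chance imbalance in stage. Step 7 describes the error in an unlucky single trial, not a bias on average.
- **That the treatment effect is diluted.** The plan states its effect as medians. With a common HR r within stage, the experimental curve at time t equals the control curve at rt, so the medians stay at 39 and 39/r = 56. What differs is the marginal against the stage-conditional hazard ratio, and 13.2 names no hazard ratio.
- **That a loss of 1 to 7 points is established.** It depends on a stage hazard ratio the documents do not give. If stage IIB and III differ little, almost nothing is lost.
- **That power necessarily falls below 80%.** At stage HR 1.5, with 430 patients and no loss, the plain test still has 80.1%.

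Two practical objections stand. A change of statistic must deal with the interim looks, and adding centre strata on top would use up most of the gain.

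**Conclusion.** This is an efficiency point about a valid test. What rests on the documents is that the stated test names no stratum or covariate, that stage is known for every patient before allocation, and that stage is not a randomisation factor. The size rests on assumptions: about 1 to 7 points of power for a stage hazard ratio of about 1.5 to 2.5, under 1 point at 1.3 or below, and about 7 to 10 at 3.0, with proportional treatment effects within stage and 30% to 70% of patients in stage III. The change is worth making because it costs almost nothing and, in the simulations, loses no material power even when stage matters little. Confidence is high on the structure and direction, moderate on the size.

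**What to change.** In 13.2, before any by-arm results are released:

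- Make the primary OS comparison a log-rank test stratified by clinical stage (IIB vs III), or the equivalent Cox test of arm adjusted for stage. Name one of the two.
- Use the stage recorded before randomisation, not the re-staging after chemoradiotherapy (10.1.8) or the pathological stage, both of which treatment can change.
- Report the stage-adjusted hazard ratio with its confidence interval, and keep the unadjusted log-rank test and the Kaplan-Meier estimates as a sensitivity analysis.
- Use the same statistic at any formal look still to come (13.5.3 dates the looks 1 June 2011 and 31 December 2015). If the first look used the plain test, the mismatch can matter little, since that look is allotted only 0.000527 (13.4).
- Do not cross stage with the eight centres. This does not settle whether centre should be allowed for in some other way.

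**Cost.** A short amendment to 13.2, matched in the SAP; no new data and no extra patients. Section 13.5.2 limits access to the data to the monitoring committee until release, so the choice can be made without knowledge of results by arm. The small downside is that the adjusted hazard ratio is conditional on stage and differs from the marginal one, which the report should say.
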